7.4 Harms

Safety information will be collected for the intention-to-treat population by recording severe adverse events (SAEs). Upon confirmation, the severity of the AEs will be evaluated for the procedures conducted, the outcomes and the relationships to the study drugs. The AEs will be reported to the principal investigator who will confer with an independent monitoring committee whose members will not know the trial-group assignment. The monitoring committee will evaluate the trial safety and, independently, will determine any necessary revisions to the trial design and will validate all decisions for continuing the trial.

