6.3 Blinding

Allocation concealment will not be blinded to the group of the assignment.

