7.3 Data monitoring

An Independent Data Monitoring Committee will carry out interim analyses every 12 months. Data will be presented to the Trial Steering Committee. The interim analysis will be performed on the primary end point when 50% of patients will be randomized and completed 6 months of follow-up. The interim analysis will be done by the Coresearch Agency that is an independent statistician company, blinded for the treatment allocation.

In presence of therapy benefit or futility in the experimental arm, the Independent Data Safety Monitoring Board Committee will report to the Central Ethics Committee the interruption of the study.

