8.7 Access to data

Prior the main publication only the Steering committee will have access to the overall results. Then, all the investigators will have access to the full dataset after a formal request describing the research.

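### Sections 7.3 and 7.4 blind the monitoring committee and interim analyst to allocation yet require decisions about the experimental arm, and 7.3 sets no limit on the interim data shown to the Steering Committee

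*Protocol*

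**What the plan says.** Section 3 of the protocol describes two open-label randomised trials. Section 6.3 confirms in its own terms that treatment is not masked: "Allocation concealment will not be blinded to the group of the assignment".

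For monitoring, the protocol sets these rules:

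- **Who is blind.** Section 7.4 describes the principal investigator as the one "who will confer with an independent monitoring committee whose members will not know the trial-group assignment". Section 7.3 adds: "The interim analysis will be done by the Coresearch Agency that is an independent statistician company, blinded for the treatment allocation".
- **What must be decided on efficacy.** Section 7.3 has the monitoring board report interruption of the study to the Central Ethics Committee "In presence of therapy benefit or futility in the experimental arm".
- **What must be decided on safety and design.** Section 7.4: "The monitoring committee will evaluate the trial safety and, independently, will determine any necessary revisions to the trial design". The same sentence has the committee validate every decision to continue.
- **Who receives interim data.** Section 7.3: "Data will be presented to the Trial Steering Committee". It does not say whether these data are pooled or by arm.
- **Who sees results before publication.** Section 8.7: "Prior the main publication only the Steering committee will have access to the overall results".

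The protocol mentions no coded arms, no route to unmasking, no closed report and no limit on what the Steering Committee is shown.

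**The concern.** A committee can act on benefit or futility in a named arm only if it knows which arm that is. The same is true of safety, because the main contrast in both trials is exposure to corticosteroids. In ACIgAN, methylprednisolone pulses with oral prednisone are compared with RASBs alone for the first 4 months. In CHRONIgAN, prednisone is compared with dapagliflozin after the 4-month run-in, and avoiding steroid side effects is part of the stated primary objective (section 2.1). A committee that cannot attribute an imbalance to an arm is poorly placed to protect participants.

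The second concern runs the other way. Treatment is open label and RASBs are titrated to response (section 3). If the Steering Committee sees comparative interim results, they could influence how the trial is run, and a later design change could be driven by the data. The text as written does not prevent this.

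**Working it through.** **1. The rules side by side**

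| Body | What it may know | What it must do | Section |
|---|---|---|---|
| Statistics company | Not the allocation | Run the interim analysis of the primary endpoint | 7.3 |
| Monitoring committee or board | Not the assigned group | Act on benefit or futility in the experimental arm; evaluate safety; determine design revisions; validate continuation | 7.3, 7.4 |
| Trial Steering Committee | Interim data, content unrestricted; overall results before publication | Receive them; no task stated | 7.3, 8.7 |

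The second row cannot be carried out as written. The first row is possible only with coded arms, since the primary endpoint is a between-arm difference (sections 4.4 and 6.4).

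**2. Reproducing the plan's own figure.** It is not in dispute; it supplies the inputs for step 3. Section 6 gives ACIgAN a difference of 1.2 − 0.6 = 0.6 g/24 h, SD 1.0, two-sided 0.05, 90% power and 10% dropout.

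- n per arm = 2 × SD² × (1.960 + 1.282)² / 0.6² = 58.4, so 59.
- 59 / 0.90 = 65.6, so 66 per arm and 132 in total. This matches the protocol.

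**3. Efficacy with coded arms.** Half of 132 is 66, or 33 per arm if there is no dropout.

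- SE = 1.0 × √(2/33) = 0.246.
- Z = 0.6 / 0.246 = +2.44 if the difference favours the experimental arm, and −2.44 if it goes against it.
- With 10% dropout (29.7 per arm), |Z| = 2.31.

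A reader who does not know which code is which sees the same size of difference in both cases. One would be a signal of benefit and the other of harm.

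**4. Safety.** The protocol gives no event rates, so these pairs are assumptions for illustration, applied to the same 66 patients.

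| Experimental v control SAE rate | Pooled rate | Expected events in 66 |
|---|---|---|
| 10% v 10% | 10% | 6.6 |
| 15% v 5% | 10% | 6.6 |
| 18% v 2% | 10% | 6.6 |
| 5% v 15% | 10% | 6.6 |

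- Pooled review cannot tell any of the four apart.
- Coded review separates the first row from the others, but cannot tell 15% v 5% from 5% v 15% by arm.
- At full ACIgAN enrolment, an assumed 8 v 2 events is 8/66 = 12.1% v 2/66 = 3.0%. Pooled, it is 10/132 = 7.6%, the same as 5 v 5.

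**5. The Steering Committee.** Section 7.3 presents data to it in the sentence that follows the interim analyses and does not restrict their content. Section 8.7 does not say when access to overall results begins. Neither section excludes comparative interim data.

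**The case against.** The strongest reply is that the blinding may mean coded groups. An interim analysis of a between-arm difference needs the groups separated, so pooled efficacy data are unlikely, and an 8 v 2 split would be visible under coding. A committee charter, not shown, could also hold an unmasking route. This stands against any statement that harm is certainly masked, which a reader might infer: neither section says the data are pooled. It does not remove the conflict. Coding still leaves the committee unable to name the experimental arm, and a charter that unmasked members would contradict section 7.4.

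Other stronger readings are tempting but not supported:

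- *The blinded statistician decides on benefit.* Section 7.3 has the company only run the analysis; the board acts on it.
- *The Steering Committee sees by-arm results about five times.* That count takes the yearly schedule over roughly six years. Section 7.3 also describes a single analysis at 50% randomised with 6 months of follow-up, and never says the data are by arm.
- *Section 8.7 gives the Steering Committee interim results.* Its most natural reading is final results before publication. It should simply say so.
- *The blind must fail as soon as the investigator confers with the committee.* Attribution of an event to a study drug may reveal the arm, but the protocol does not say what is passed on.

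Two further points stand. Sections 5.3.8 and 5.3.9 give separate routes for SAEs and SUSARs, so harm is not invisible, although those routes provide no comparison by arm. And the SAE illustration rests on assumed rates and small numbers: even 8/66 v 2/66 gives Fisher p = 0.096.

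**Conclusion.** The conflict holds on the protocol's wording. Sections 7.3 and 7.4 withhold allocation from the people who must act on it, and 7.3 places no limit on the interim data given to the Steering Committee of an open-label project. How much is lost depends on what blinding means here. With pooled data an imbalance in harm would be hidden; with coded arms it would be seen but not attributed. In either case, benefit or futility in the experimental arm cannot be identified. The arithmetic illustrates this using the protocol's ACIgAN planning values and assumed event rates; no stated figure is wrong. The Steering Committee part is a risk left open by the wording, not a demonstrated release of comparative results. The point should be corrected, because it touches participant protection and trial integrity and the change is small.

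**What to change.** - **Sections 7.3 and 7.4:** remove the monitoring committee's blinding. State that it receives efficacy and safety by identified arm, separately for ACIgAN and CHRONIgAN, in a closed report.
- **Section 7.3:** replace the sentence on presenting data to the Trial Steering Committee with one saying that it receives the monitoring committee's recommendation and pooled conduct data only.
- **Section 8.7:** state that Steering Committee access to overall results begins after database lock.
- **Section 7.4:** state that any design revision made by people who have seen by-arm results is limited to safety or stopping.

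The cost is protocol and charter wording. The one practical consequence is that whoever prepares the closed report must know the arms and be kept apart from trial-conduct decisions. The approval pages list the same statistics company under epidemiology and data analysis, so the sponsor should state how that separation is kept. Whether to use a different statistician, or to move design decisions to another body, is the sponsor's choice and is not needed to remove the conflict.

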7.5 Site monitoring and audits

Before study initiation, at a site initiation visit or at an investigator's meeting, Sponsor personnel (or designated CRO) will review the protocol and the eCRFs with the investigators and their staff. During the study, the field monitor will check the completeness of patient records, the accuracy of entries on the eCRFs, the adherence to the protocol to Good Clinical Practice, the progress of enrollment, and to ensure that study treatment is being dispensed and managed according to specifications. Key study personnel will be available to assist the field monitor during the visits/webinars. The investigator will maintain source documents for each patient in the study, consisting of case and visit notes (hospital or clinic medical records) containing demographic and medical information, laboratory data and the results of any other tests or assessments. All information recorded on eCRFs will be traceable to source documents in the patient's file. The investigator will also keep the original signed informed consent form (a signed copy will be given to the patient). The investigator will give the monitor access to all relevant source documents to confirm their consistency with the eCRF entries. The Sponsor monitoring standards will require full verification for the presence of informed consent, adherence to the inclusion/exclusion criteria and documentation of SAEs.

Source data/documents will be available to inspections by the Sponsor or designee or Health Authorities.

8. ETHICS AND DISSEMINATION

8.1 Research ethics approval

The protocol is subject to approval by the competent Independent Ethics Committee. It will be carried out according to the Declaration of Helsinki (IV adaption), to the ICH Guideline for Good Clinical Practice and the laws and regulations of the country. During the follow-up every patient will be informed about goals, expected benefits and possible risks, and rights to refuse or to withdraw at any time.

The model of informed consent that will be presented to potential participants has been prepared and approved by the Steering Committee.

8.2 Protocol amendments

Substantive amendments with protocol identifiers and dates, transparently described in the trial reports, will be submitted to the ethics committees.

8.3 Consent or assent

The written material (information leaflet and consent document) will be presented by the clinical investigators of the renal centers to the participants. After the signature of the consensus participation the patient will be enrolled and randomized separately in each trial (allocation 1 to 1 ratio) via a web-based program generating random numbers.

Additional request of consent will be done for the collection of biological samples (blood, urine and kidney tissue) that will be used for the ancillary study “Cutting-edge bio-molecular analysis for precision therapy in IgAN (BIO-D).

8.4 Confidentiality

Every enrolled participant will be identified by a personal code connected to the code of the renal centre. Thus, depersonalized data will circulate for the monitoring of the clinical study. Encrypted digital code will be stored by the renal centers. Information about study subjects will be kept confidential and managed under the applicable laws and regulations.

8.5 Insurance

The Sponsor has taken out a liability insurance policy covering this clinical trial. This insurance policy is in accordance with local laws and requirements. The insurance of the Sponsor does not relieve the Investigator and the collaborators from maintaining their own liability insurance policy.

8.6 Declaration of interests

Clinical and scientific partners do not have conflict of interest in the publication of data.

8.7 Access to data

Prior the main publication only the Steering committee will have access to the overall results. Then, all the investigators will have access to the full dataset after a formal request describing the research.

8.8 Ancillary and post-trial care

Ancillary project. BIO-D study

8.9 Dissemination policy

The plan to disseminate trial results to key stakeholders will be based on the presentation of data to National and International Congresses and on the submission of papers to international scientific journals. Furthermore, dissemination of data will be done by websites. The plan will be discussed with the Steering Committee.

Sharing of data will be established by the Steering Committee.

9. ANCILLARY PROJECT

A cutting edge-molecular study will be conducted in a cohort of 120 enrolled IgAN patients with active or chronic/moderate renal lesions to evaluate the molecular effect of personalized therapy (BIO-D)

9.1 Background

Immunoglobulin A nephropathy is characterized by recurrent episodes of macrohematuria in concomitance of upper respiratory tract infections or other mucosal infections, or by permanent microhematuria. The diagnosis is based on the presence of IgA deposits in the mesangium of glomeruli. A “score system” is used for the histological analysis of the kidney biopsy (6-8). Five types of renal lesions are scored: Mesangial hypercellularity (M 0,1), Endocapillary hypercellularity (E 0,1), Segmental glomerular sclerosis (S 0,1), Tubular atrophy/interstitial fibrosis (T 0,1,2), and Extracapillary proliferation, crescents (C 0,1,2). IgAN is characterized also by increased serum levels of galactose-deficient IgA1 (Gd-IgA1) (54).

We have studied the gene expression in leukocytes isolated from the blood samples of IgAN patients and evidenced differentially expressed genes (DEGs). Bioinformatic analysis discriminated 210 DEGs and functional analysis, operated on the top selected genes, demonstrated that WNT-B-catenin and PI3K/Akt pathways were highly activated in IgAN patients (55). Furthermore, DEGs were also found in monocytes isolated from the blood of IgAN patients and primarily involved genes belonging to the apoptosis signaling, mitochondrial dysfunction and TNFR2/1 were found (56). We also focalized the attention on gross hematuria episode in concomitance to mucosal infections and DEGs were involved in interferon signaling and antigen presentation (57).

Recently, we have evidenced specific DEGs that characterize active renal lesions (E1 and C1,2) compared to chronic renal lesions (T1,2) in kidney biopsy specimens of IgAN patients (58). Bioinformatic analysis has identified transcripts for active (DEFA4, TNFAIP6, FAR2) and chronic (LTB, CXCL6, ITGAX) renal lesions that were validated by RT-PCR and IHC. Finally, two DEGs (TNFAIP6 for acute and CXCL6 for chronic renal lesions) were confirmed in the urine of an independent cohort of IgAN patients compared with non-IgAN patients and controls. In conclusion, we have discovered two urinary biomarkers that may be used for specific clinical decision making during the clinical course of the disease.

Recently, we have obtained preliminary data on gene expression in microvesicles isolated from the urine of patients with IgAN (unpublished data). This means that we have set-up all techniques for the study of transcriptomics in the three compartments of the body (blood, kidney, urine) in IgAN patients with active renal lesions at kidney biopsy and in IgAN patients with chronic renal lesions enrolled in the CLiGAN study.

In conclusion, the CLiGAN study includes a transcriptomic study carried out on the three compartments (blood, kidney and urine) of the IgAN patients at the time of the kidney biopsy and during the follow-up. We will analyze transcriptome changes of peripheral blood mononuclear cells and urinary microvesicles during the clinical course of the disease separately in the two subgroups of patients. This scientific approach will allow a finer molecular stratification of patients and the

identification of specific diagnostic biomarkers that could be used for a precision therapy in IgAN patients.

9.2 Aim

Aim of this research project is to integrate transcriptomic results obtained from all three compartments (blood, kidney and urine) in the same patient at the time of the kidney biopsy and then during the follow-up to evaluate the benefit of corticosteroids and the benefit of Dapagliflozin combined with RASBs in patients with active renal lesions and RASBs in patients with chronic or moderate renal lesions. We will analyze transcriptome changes during the clinical course of the disease separately in the two subgroups of IgAN patients. Blood and urine samples will be taken on the same day. This scientific approach will permit a finer molecular stratification of IgAN patients and the identification of specific biomarkers that could be exploited for the identification of novel therapeutic targets and the benefit of personalized therapy.

9.3 Objectives

- To obtain a finer molecular stratification of patients with active and moderate/chronic renal lesions.
- To identify specific diagnostic biomarkers that could be used for precision therapy in IgAN patients.

9.4 Endpoints

Biomarker analysis on patients' biological samples evaluating:

Blood samples

- the measurement of IgA, Gd-IgA1, Gd-IgA1-specific IgG, Gd-IgA1-specific IgA, Gd-IgA1-IgG immune complexes.
- gene expression pattern in PBMCs from patients with active or chronic/moderate renal lesions

Urine samples

- transcriptomic analysis in urinary cells
- transcriptomic analysis on isolated microvesicles

Tissue sample

- transcriptomic pattern on RNA extracted from kidney tissue in patients with active or chronic/moderate renal lesions

9.5 Collection of biological samples

In this project we will collect blood, kidney biopsy and urine samples from IgAN patients with acute renal lesions enrolled in the ACIgAN clinical study and from IgAN patients with chronic and moderate renal lesions enrolled in the CHRONIgAN trial. Blood and urine samples will be collected

in every patient on the same day before kidney biopsy will be performed and then during the clinical course of the disease. IgAN patients will be accurately stratified by the MEST-C classifications.

Blood and urine samples will be collected at different time (T) from patients during the follow-up of the CLlIgAN study:

- i) patients with active renal lesions: T0,T1,T2,T4,T6, T8,T12,T24, T36 months and
- ii) in patients with chronic and moderate renal lesions: T0,T1,T4,T8,T10,T14,T24,T36 months.

Blood samples. 10 ml of blood will be collected in PAXgene tubes for the isolation of peripheral blood leukocytes that will be used for transcriptomic studies.

Serum samples will be collected for the measurement of IgA, Gd-IgA1 and other biomarkers. Some of these biomarkers have been described as predictors of clinical outcome but none has been validated in prospective clinical studies. Therefore, we will measure some current biomarkers involved in the pathogenesis of the disease as Gd-IgA1 during the follow-up.

Urine samples. 30-50 ml of urine of the second morning urination will be collected for the isolation of urinary microvesicles.

Renal biopsy will be used for histological diagnosis and immunofluorescent technique. Then, transcriptomics will be performed in RNA eluted from 5 micron thickness sections for a total of 8 slides.

9.6 Methods

All samples will be stored in freezer at -20° or -80°C in the participant renal centers. Every six months, or when possible, the collected biological samples will be shipped to the [name] Foundation for the molecular study. Shipping fees will be supported by the Foundation.

Transcriptome analysis will be done using single cell or nuclear cell RNA-sequencing.

9.7 Statistical analysis

Data from transcriptomics will be elaborated by computational analysis and artificial intelligence (artificial neural networks and deep learnings).

Integrative analysis of transcriptomic data will be done combining response to the combined therapy (Corticosteroid and RASBs) in IgAN patients with active renal lesions and to the combined therapy (Dapagliflozin and RASBs) in patients with chronic or moderate renal lesions.

9.8 Consent or assent

Additional request of consent will be done for the collection of biological samples (blood, urine and kidney tissue) that will be used for the ancillary study “Cutting-edge bio-molecular analysis for precision therapy in IgAN (BIO-D).

9.9 Where the research will be conducted

Biological samples will be collected in the nephrology centers and analyzed at laboratories of Scena Foundation. Every six months the collected biological samples will be shipped to the Scena Foundation for the molecular study. Shipping fees will be supported by the Foundation.

The Scena Foundation is located in the Department of Emergency and Organ Transplantation, Policlinic, University of Bari, which has multiple fully equipped modern molecular biology research laboratories containing analytical and genomic facilities in order to perform all the analysis. Single cell RNA-sequencing (sc RNA-seq) and computational analyses will be done in collaboration with the Department of Molecular Biology of the Bari University.

9.10 Dissemination policy

The plan to disseminate trial results to key stakeholders will be based on the presentation of data to National and International Congresses and on the submission of papers to international scientific journals. Furthermore, dissemination of data will be done by websites. The plan will be discussed with the Steering Committee.

Sharing of data will be established by the Steering Committee.

